7.2 Statistical Methods

For caries arrest, we will first determine the per-patient proportion of carious lesions treated with simple versus complex prevention that stayed arrested throughout the length of the study. The percentage of arrested caries (at the child level) will be modeled using multilevel binomial regression. Our noninferiority margin, δ , is set at 10%. Our null hypothesis is that simple prevention is not inferior to the complex prevention by at least δ : π_{simple} - $\pi_{\text{complex}} \ge \delta$. Our alternative hypothesis is that π_{simple} - $\pi_{\text{complex}} < \delta$. We will use differences in effect sizes as estimated by confidence intervals to determine clinical non-inferiority of the two prevention methods. For the prevention of new caries, we will use generalized estimating equations (GEE) with a logit link (caries prevalence) and a negative binomial link (caries incidence), assuming an exchangeable correlation matrix, to evaluate longitudinal effects of comprehensive care untreated decay. We will identify the number of teeth at risk for each child during each follow-up interval and determine the number of those teeth in which new caries is observed at the examination that ends that interval. Primary teeth lost in each interval and new permanent teeth will not contribute to data for that interval. To explore non-linear trends in untreated decay between simple and complex prevention, we will use generalized additive models (GAMs) with non-parametric smoothers. Longitudinal effects of simple and complex prevention on academic outcomes, compared to untreated children, will be analyzed using propensity score-matching and multilevel modeling. First, we will estimate propensity scores for each participant at baseline, establishing the probability of treatment assignment conditional on observed covariates (e.g., prior academic performance). Propensity scores will be used to match treatment students to students not receiving treatment, considering multiple forms of matching
such as nearest neighbor and caliper. Treated students and matched comparators will then be analyzed using multilevel mixed effects linear regression (for academic achievement) and Poisson regression (for school absences).

Longitudinal effects of simple and complex prevention on dental-related service use and costs among Medicaid participants, compared to children in non-participating schools, will be analyzed using difference-in-differences analysis and propensity score matching. The propensity score weighting will be used to match children in participating schools to children in non-participating schools to account for any selection impacting whether a child is at a school participating in the Caried*Away* programs. The propensity score weighting will be used to account for student-level and school-level characteristics impacting whether the student is at a school participating in the Caried*Away* programs.

We will then adapt a published Markov model in combination with threshold analysis to compare the simple and complex prevention programs relative to non-participating schools in net costs and quality-adjusted life-years to determine the cost-effectiveness and budget impact of all three options (simple prevention, complex prevention, no prevention).

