1.2 Study Aims

The overall goal of this study is to measurably improve oral health equity. Towards this goal, we will compare "simple" and "complex" prevention, two packages of interventions designed to prevent and arrest dental caries. The study design is a cluster randomized non-inferiority pragmatic trial. Both preventive interventions are expected to be equally effective in improving health equity. The major difference in the two protocols is that "simple" prevention costs

approximately 25% of "complex" prevention. Simple also takes approximately 25% of the time of complex prevention. Therefore, if simple and complex are found to be equally effective, for the same time and cost, simple prevention could improve health and health equity to approximately 3 times the number of children as complex prevention.

Our prior work, and data from systematic reviews, indicates that the protocols we propose should be similarly effective in both arresting current caries and preventing subsequent caries by 50% to 80%. Thus all children should benefit from the proposed preventions. We will collect data on oral health and child quality of life, and assess student academic performance.

The study consists of three groups: (1) a group receiving simple prevention twice per year; (2) a group receiving complex prevention twice per year; and (3) a group receiving simple prevention once per year.

We will select 76 elementary schools to participate in the program over a five-year period. 30 elementary schools will be randomized to receive simple prevention twice per year and 30 elementary schools will be randomized to receive complex prevention twice per year. The remaining 16 schools will receive simple prevention once per year. The care will be provided in schools, community-based locations or at the New York University College of Dentistry.

The inclusion criteria for the schools enrolled in groups (1) and (2) include: A Hispanic/Latino population of at least 50% and a free and reduced lunch population of at least 80%. The remaining racial/ethnic and socioeconomic distribution of these schools will include children from any race/ethnicity and economic background. The inclusion criteria for schools in group (3) include any elementary school in New York City and will be selected to include representation from every major racial/ethnic group and socioeconomic level.

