For the purposes of the analysis on dental-related service use and costs among Medicaid beneficiaries, all children participating in Medicaid of elementary school age will be included in the analysis, except for children in participating schools that do not provide informed consent to provide oral health and Medicaid dental service use data.

The Primary Specific Aims are to:

- 1. Determine the non-inferiority of simple vs complex caries prevention for preventing new caries (primary prevention).
- 2. Determine the non-inferiority of simple vs complex caries prevention for arresting current caries (secondary prevention).
- 3. Determine the impact of simple vs complex prevention on child oral healthrelated quality of life
- 4. Determine the impact of once per year vs twice per year care on the arrest and prevention of caries

Notably, toothaches or office based dental care reduces in-class learning time. If the caries prevention programs are as effective as predicted, knowing the time/trade-off will be important. Thus a secondary outcome of the study will be school performance (school absence and student achievement). To insure accurate assessments, program participants will be compared to children in their own schools and to children in NYC "peer schools" not participating in the study. No additional data is collected for educational outcomes from participants.

The Secondary Specific Aims are to:

- 1. Determine the impact of prevention vs no prevention on school absence
- 2. Determine the impact of prevention vs no prevention on standardized test performance
- 3. Determine the impact of simple vs complex prevention on school absence and test performance

The exclusion criteria will be those: (1) not attending participating schools, (2) those attending participating schools without informed consent, or (3) those attending participating schools with informed consent, but without assent and (4) those allergic to silver.

For the purposes of the analysis on dental-related service use and costs among Medicaid beneficiaries, the only excluded groups are (1) children not participating in Medicaid will be excluded and (2) children participating in Medicaid in Caried*Away* schools, but without informed consent to provide oral health and Medicaid dental service use data.

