NYUCD licensed dentists, dental hygienists, nurses, and/or advanced level dental hygiene students supervised by licensed dental professionals will provide care to participating students at all locations. All clinical personnel providing care will wear PPE based on current NYU Dentistry guidelines. PPE is listed below:

- 1. Disposable gowns
- 2. Disposable gloves
- 3. N95 respirator that have been fit tested for a specific respirator and shall be disposed of at the end of each clinical day
- 4. Level 3 surgical masks
- 5. Goggles
- 6. Face Shields
- 7. Bonnets
- 8. Booties

Gloves are changed between patients. Goggles and face shields are disinfected between patients. All dental chairs, stools and touch surfaces are disinfected at the beginning of each day, prior to and after treating patients, and at the end of the day.

Caried*Away* school COVID-19 Checklist: The first day of the school visit the NYUCD HCP will review the school's policies for prevention of coronavirus transmission among students, staff and faculty using the Caried*Away* School COVID-19 Checklist. If there is any reason to believe that schools policies would put NYUCD HCP or students at risk, the NYUCD HCP Dental will contact the Principal Investigator to determine the appropriate course of action.

Consenting students in participating schools will receive care in a school, at a community-based location, or at NYUCD. Randomization will be done by computer and remain in effect during the duration of the trial. Care will be provided in a school, community-based locations or at NYUCD according to the group selection as described above. Participants in their first and second year will contribute data to evaluate caries arrest. We will follow them longitudinally to evaluate prevention of new caries. The total expected school enrollment for the clinical and community components of the study is 76 schools.

Hypotheses and Interventions: We will test the primary hypothesis that school or communitybased "simple" caries arrest and prevention provided twice yearly is equally effective (noninferior) as school or community-based "complex" caries arrest and prevention provided twice yearly.

- "Simple" prevention is defined as fluoride varnish, silver diamine fluoride, fluoride toothpaste and oral hygiene instruction.
- "Complex" prevention is defined as traditional sealants, interim therapeutic restorations, fluoride varnish, fluoride toothpaste and oral hygiene instruction.

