3.2 Primary Study Endpoints

Caries arrest and prevention will be determined at each visit. The primary end point for caries arrest will be at 2 years, and follow on to termination of trial determine the length of time that caries remains arrested. The primary end point for caries prevention will be at 3 years, and follow on to termination of trial to determine stability of prevention.

Presence / absence of caries is assessed by visual/tactile methods. Sound tooth surfaces appear white and smooth. Active caries appear brown and soft. Arrested caries appear dark brown or black and hard.

For clinical assessment, we will train and standardize clinicians using validated criteria implemented by the Centers for Disease Control and Prevention (CDC) in the National Health and Nutrition Examination Surveys (NHANES). Training and validation were developed and documented by our Colleague, [name], while at the CDC and field tested in the examination of special athletes^{23,24}. Training and standardization of these examiners implement the World Health Organization guidelines^{25,26}.

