6.2 Preventive Care

6.2.1 Simple prevention

Consists of a gentle toothbrush cleaning, oral hygiene instruction, an examination, delivery of silver diamine fluoride applied to all pits and fissures on bicuspids or molar teeth, and to all posterior, asymptomatic carious lesions. Fluoride varnish is then applied. Each child is given a small bag with a toothbrush, fluoride toothpaste, and a note indicating the results of the examination, the care provided, and a list of local dentists or community health centers for follow on care.

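### The arrest outcome in section 7.2 has no defined lesion cohort, no per-lesion clock and a time window that conflicts with section 3.2, so lesions with unequal follow-up can be pooled and the non-inferiority contrast biased

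*Combined protocol and SAP*

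**What the plan says.** - **Analysis (7.2).** The child-level outcome is built as follows: "we will first determine the per-patient proportion of carious lesions treated with simple versus complex prevention that stayed arrested". The success criterion is that the lesions "stayed arrested throughout the length of the study". No date of first treatment, time origin or minimum follow-up is given for a lesion.
- **Endpoint (3.2).** "The primary end point for caries arrest will be at 2 years", with later follow-up to see how long arrest lasts. The section also states: "Caries arrest and prevention will be determined at each visit".
- **Who contributes (3.1).** "Participants in their first and second year will contribute data to evaluate caries arrest"; the section says this again further on.
- **Schedule and care.** Both randomised arms are seen twice a year (1.2). Simple care includes application "to all posterior, asymptomatic carious lesions" (6.2.1). Section 6.2.2 has a parallel statement for complex care, without the restriction to posterior teeth.
- **Contrast with prevention.** For new caries, 7.2 does define teeth at risk per follow-up interval and excludes primary teeth lost in the interval. It gives no equivalent rule for arrest.

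**The concern.** The two time windows cannot both hold. Follow-up runs to 5 years for the first 30 randomised schools and 4 years for the second 30 (4.2.2), so arrest lasting the whole study is a different quantity from arrest at 2 years.

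The lesion set is also open. Taken literally, a lesion first found active and treated at 6, 12 or 18 months enters the proportion with the same weight as one treated at entry, although it has had 1.5, 1 or 0.5 years to fail by the child's 2-year examination. On the whole-study reading the spread is wider.

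How many late lesions a child acquires is an outcome of the prevention component. The arrest denominator therefore depends on something that happens after randomisation, and it ties one primary outcome to the other. At stake is whether the arrest contrast compared with the 10-point margin estimates the 2-year difference that section 3.2 promises.

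**Working it through.** **The plan's own figure.** With 20% arrest in both arms, a 10-point margin, one-sided 5% and 80% power: n = 2 × 0.20 × 0.80 × (1.645 + 0.842)² / 0.10² = 198 per group. The design effect is 1 + (235 − 1) × 0.10 = 24.4, and 396 × 24.4 = 9,662. Both figures in 7.1 reproduce if the 5% is one-sided, which the plan does not state. Lesion follow-up time is not an input. The implied standard error of the difference is 10 / (1.645 + 0.842) = 4.02 points, held fixed below.

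**Assumptions not in the documents.** There are m = 2 lesions per affected child at entry and r = 0.1, 0.2 or 0.4 new lesions per child-year, treated equally at 6, 12 and 18 months. Arrest is cumulative. The 40% of children affected at entry is from 7.1. Lesions are weighted equally, which only approximates a per-child proportion.

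**Late share.** w = 1.5r / (0.4m + 1.5r) = 15.8%, 27.3% and 42.9%. With m from 1.5 to 3 the range is 11% to 50%.

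**Arrest by follow-up time, constant failure rate.** S(t) = p^(t/2), where p is 2-year arrest.

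| p | 0.5 y | 1 y | 1.5 y | 2 y | mean of late lesions |
|---|---|---|---|---|---|
| 80% | 94.6 | 89.4 | 84.6 | 80.0 | 89.5 |
| 70% | 91.5 | 83.7 | 76.5 | 70.0 | 83.9 |
| 20% | 66.9 | 44.7 | 29.9 | 20.0 | 47.2 |
| 10% | 56.2 | 31.6 | 17.8 | 10.0 | 35.2 |

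**Pooled deficit and error, equal late shares.** Deficit = (1 − w) × 10 + w × D, where D is the arm difference among late lesions: 5.65 points at 80% against 70%, and 11.95 at 20% against 10%. False non-inferiority = 1 − Φ(1.645 − (10 − deficit)/4.02). Example at 80% against 70% with w = 27.3%: 7.27 + 1.54 = 8.81 points, and 1 − Φ(1.645 − 1.19/4.02) = 8.9%.

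| Scenario (true deficit 10 points) | Apparent deficit | False non-inferiority |
|---|---|---|
| 80% v 70%, constant rate | 9.3 to 8.1 | 7.0% to 11.9% |
| 80% v 70%, half the failure early on the log scale, S(t) = p^(0.5 + t/4) | 9.7 to 9.2 | 5.8% to 7.6% |
| 80% v 70%, all failure early | 10.0 | 5.0% |
| 80% v 70%, initial arrest 90% v 78.75%, equal later rate | 10.1 to 10.3 | 4.8% to 4.4% |
| 20% v 10%, constant rate | 10.3 to 10.8 | 4.3% to 3.2% |

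**Unequal late shares (assumed).** Complex has r = 0.1 or 0.2, simple has 1.5 or 2 times as many, and the failure rate is constant.

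| True arrest | Apparent deficit | False non-inferiority |
|---|---|---|
| 80% v 70% | 8.5 to 6.7 | 10% to 21% |
| 20% v 10% | 8.8 to 6.6 | 9% to 21% |

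With equal true arrest of 80%, the imbalance alone favours simple by (difference in w) × (89.5 − 80.0): 0.6 to 1.5 points.

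**The case against.** The case against has force on four points.

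1. **Pooling is not an express rule.** A reader might infer that the plan definitely counts every lesion ever treated in its 2-year result. No section says so. Aim 2 in 1.2 and Table 1 speak of current caries, which could mean caries present at entry, and 3.2 hints at a durability measure. Neither settles the matter. What stands is that the operative sentence in 7.2, followed literally, admits late lesions.
2. **Dilution is not general.** A reader might infer that mixed follow-up always shrinks a true deficit. At 20% arrest, the only level used to size this endpoint, equal late shares with a constant failure rate make the deficit larger and the test conservative. The 50% to 80% figures in 1.2 and 1.4.3 describe expected benefit in broader terms and are not the planning value for arrest. The failure shape matters as much: if lesions either arrest early or never do, follow-up length has no effect. If arrest were scored as current status and built up with repeat application, short follow-up could lower the proportion.
3. **More new lesions in simple is an assumption.** A reader might infer that simple stands to gain. The documents give no imbalance, and 6.4 expects similar effects. A large prevention deficit would also be tested directly, since prevention is primary too. What stands is that equality on the other primary question cannot be presumed when defining this one. With continuing failure, the gain to the arm with more late lesions appears at both high and low arrest.
4. **The new-lesion rates have no source in the documents.** This is conceded; the figures are scenarios.

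**Conclusion.** The point holds as a defect in how the arrest outcome is defined. Sections 3.2 and 7.2 give incompatible windows. The literal text mixes lesions of unequal follow-up and cannot yield the stated 2-year result. Its denominator also responds to treatment after randomisation.

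Bias in the non-inferiority contrast is possible, but neither its size nor its direction is established. With equal late shares, the scenarios put false non-inferiority between about 3% and 12% against a nominal 5%. It reaches 21% only with an assumed excess of new lesions in simple and a constant failure rate. These figures rest on the late share, the failure shape, cumulative scoring and a one-sided 5% test. The required sample size of 9,662 does not change. This is a low-cost improvement worth making before analysis, not evidence that the trial will reach a wrong conclusion.

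**What to change.** In 7.2, define the primary arrest outcome on lesions that are active and first treated at the child's first treatment visit, scored at the examination 2 years after that visit. Report lesions first treated later in a secondary analysis by time since each lesion's first treatment. State how primary teeth shed before 2 years are handled, because the tooth-loss rule in 7.2 covers new caries only. Align 3.1 (both statements about years 1 and 2), 3.2 and 7.2 on the same window.

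The cost is plan wording and a first-treatment date per lesion, which the visit-level electronic records should provide. The downside is fewer lesions, and children whose first lesion appears after entry leave the primary arrest analysis. The 24.4 design effect should not be cited to show that the precision loss is modest, because it assumes all 235 enrolled children per school contribute. With 40% affected, 0.40 × 235 = 94 per school and the design effect is 1 + 93 × 0.10 = 10.3.

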The study administrator will then cross-reference the OSIS number in the original .csv file which was provided to us at the beginning of each school year by the NYC Department of Education, and verify that the correct OSIS number was provided correctly by the consenter.

The study administrator then uploads all of the informed consent PDF's to NESS via the secure and password protected ShareFile link listed below:

• https://nedental.sharefile.com

NESS then uploads each student's eICF to their electronic dental record in the iPad.

Examination, preventive care, and data collection by a proprietary secure electronic health record will be provided and collected up to 5 years, and all children in a given school will receive the same preventive care at the same frequency either at the school, at a community-based location or at NYUCD. Participants in their first and second years will contribute data to evaluate caries arrest, and then they will be followed longitudinally within schools. 50% of children ≥ 8 years old will be assessed with a validated quality of life instrument, and all children will receive a comprehensive oral examination at each visit. We will also test the secondary hypotheses that prevention: improves school performance and is equally effective given once per year as twice per year.

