4.2.2 School Randomization

Beginning in the first year of the study, a total of 30 schools will be randomized (15 schools receiving simple prevention and 15 receiving complex prevention) to receive prevention twice per year. Consenting children will be followed over five years. In Year 2, 30 additional schools will be randomized to receive either simple or complex prevention twice per year. Consenting children will be followed over four years. Also in Year 2, an additional 16 schools will be selected to receive simple prevention once per year, and consenting children will be followed over four years.

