6.1 Description

6.1.1 Informed Consent

All students enrolled in the 76 participating elementary schools, with paper or electronic informed consent signed by the parent/guardian, will receive caries prevention currently recommended by systematic reviews and national guidelines. Care will be provided independently of a family's ability to pay. Informed consent will be active for the entire time the child is in the school. Each year any newly enrolled students at the school will have the opportunity to join the program and be enrolled in the study if the parent/guardian signs the paper or electronic informed consent. If guardianship of the child changes during this time a new paper or electronic informed consent will need to be signed. The consent form is valid for 5 years or as long as the child is in NYC schools.

To facilitate accurate informed consent and student tracking we will request student rosters from the NY City Department of Education (NYC DOE). This will facilitate tracking students longitudinally. All forms will be translated into the major languages of NYC school children's parents. Those languages are Arabic, Bengali Bangla, Chinese, English, French, Haitian Creole, Korean, Russian, Spanish and, Urdu.

Blank IRB-approved paper informed consent will be distributed during Caried*Away* community engagement events and or mailed to students at the beginning of each school year in concert with all other school notifications. Parents can also choose to sign their child up for the program at their child's school. The current IRB approved blank informed consent will include a prepopulated personalized principal recruitment letter from the principal, the parent/guardian alternate location recruitment letter, the parent/guardian recruitment flyer, program information, a health history, the NYU Langone Health COVID-19 research participant information sheet and, the blank informed consent to be filled out for signature by the parent/guardian.

Completed parent/guardian signed and dated paper informed consent will be returned to the school and collected by the research team. This protocol aligns with other school vision, hearing, and vaccination programs. Care will be provided to all children with informed consent. The information listed on the signed paper informed consent is loaded directly into the Apple password protected iPad to create the child's secure electronic dental record.

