7.3 Subject Population for Analysis

For study outcomes, participants will be analyzed using intent to treat. All participants will be analyzed as randomized in the original randomization, regardless of whether or not they received an intervention.

For dental-related service use and costs, all New York City elementary school-age children enrolled in Medicaid will be analyzed using intent-to-treat.

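### Section 7.2 measures caries arrest over the whole study while section 3.2 sets the primary arrest endpoint at 2 years, and 7.2 leaves it unclear which lesions count

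*Combined protocol and SAP*

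**What the plan says.** Section 7.2 defines the arrest variable as "the per-patient proportion of carious lesions treated with simple versus complex prevention that stayed arrested throughout the length of the study". The next sentence models that child-level percentage by multilevel binomial regression, and the 10% margin follows. Section 7.2 does not mention 2 years and defines no other arrest variable.

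Section 3.2 reads: "The primary end point for caries arrest will be at 2 years, and follow on to termination of trial determine the length of time" for which lesions remain arrested. Section 3.1 supports the 2-year window twice: "Participants in their first and second year will contribute data to evaluate caries arrest", and later "Participants in their first and second years will contribute data to evaluate caries arrest".

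On follow-up, section 4.2.2 says of schools randomized in Year 1, "Consenting children will be followed over five years", and of those randomized in Year 2, "Consenting children will be followed over four years". Section 6.1.1 adds: "Each year any newly enrolled students at the school will have the opportunity to join the program and be enrolled in the study".

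On the analysis population, section 7.3 says: "All participants will be analyzed as randomized in the original randomization, regardless of whether or not they received an intervention".

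**The concern.** Caries arrest is one of the primary outcomes on which the trial is powered. An analyst who follows 3.2 and one who follows 7.2 would derive different variables from the same records and test each against the same 10-point margin. A non-inferiority conclusion should not depend on which section is read.

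The wording of the denominator adds a second uncertainty. If *treated* refers to care that reached a particular lesion, a lesion or child left untreated drops out because of something that happened after randomization. The rule in 7.3 exists to prevent that.

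**Working it through.** **1. The plan's own figure.** Inputs from 7.1: arrest 20% in both arms, margin 10 points, alpha 5%, power 80%, intraclass correlation 0.10, 235 children per school.
- Per arm: (1.645 + 0.842)² × 2 × 0.20 × 0.80 / 0.10² = 198, so 396 in total. This matches the plan with alpha one-sided at 5%; one-sided 2.5% would give 252 per arm.
- Design effect: 1 + 234 × 0.10 = 24.4, and 396 × 24.4 = 9,662. This also matches.

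Section 7.1 attaches no time point to the 20%, so the calculation does not show which endpoint was powered. That matters: with the same margin, the total is 7,710 at 15% arrest and 12,688 at 30%.

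**2. The sections side by side.**

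| Section | Time point for arrest | Use of later follow-up |
|---|---|---|
| 3.2 | 2 years | how long arrest lasts |
| 3.1 (twice) | first and second years | longitudinal follow-up |
| 7.2 | whole study | part of the outcome itself |

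Under 4.2.2 the 7.2 window is 5 years for Year 1 schools and 4 for Year 2 schools. Under 6.1.1 it is shorter for children who join later.

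**3. Two cases.** A lesion arrested at 2 years and active again in year 3 is a success under 3.2 and a failure under 7.2. A child who joins with one year left has no 2-year examination under 3.2, yet could count as arrested throughout under 7.2.

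**4. How far apart the two outcomes could lie.** The documents give no reactivation rate. As an assumption, let an arrested lesion stay arrested at each half-yearly visit with probability s, counting 4, 8 and 10 half-years in 2, 4 and 5 years.

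| s | 2 years (s⁴) | 4 years (s⁸) | 5 years (s¹⁰) |
|---|---|---|---|
| 0.98 | 0.922 | 0.851 | 0.817 |
| 0.95 | 0.815 | 0.663 | 0.599 |
| 0.90 | 0.656 | 0.430 | 0.349 |

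This concerns the level of the outcome, not the difference between arms.

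**5. Follow-up, as an illustration only.** Section 7.1 gives 20% attrition per visit, for the prevention outcome. Suppose it applies to arrest and is permanent dropout.
- At 2 years, the fourth visit after the first: 0.8⁴ = 41% of children remain.
- At the last visit, the seventh (Year 2 schools) or ninth (Year 1 schools) after the first: 0.8⁷ = 21% and 0.8⁹ = 13%. Counting it as the eighth or tenth gives 17% and 11%.
- Children with caries per school: 235 × 0.40 = 94. At 2 years 38.5 remain, so the effective number per arm is 30 × 38.5 / (1 + 37.5 × 0.10) = 243. Power is Φ(0.10 / √(2 × 0.20 × 0.80 / 243) − 1.645) = 87%.
- At the last visit 12.6 or 19.7 remain per school, so the effective number is 15 × (5.84 + 6.87) = 191 and power is 79%.

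This reading sits badly with 7.1. Compounded dropout gives (1 − 0.8⁸)/0.2 = 4.2 visits out of 8, or (1 − 0.8¹⁰)/0.2 = 4.5 out of 10, against the plan's average of 6. If instead 20% are simply missing at any one visit, 94 × 0.8 = 75.2 children per school are seen at either time. The effective number is 30 × 75.2 / (1 + 74.2 × 0.10) = 268, and power is 89% at both. There is then no gap.

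**6. The denominator.** Sections 6.2.1 and 6.3 limit silver diamine fluoride on lesions to posterior, asymptomatic ones. For complex prevention, 6.2.2 and 6.3 state no posterior limit. On the other side, the Study Summary, 1.3 and 5.8.3 set no posterior limit on carious lesions, 5.3 puts varnish on all teeth (so every lesion might count as treated), and the relevant sentence in 6.6 is incomplete. The set of treated lesions could therefore differ between arms, but the documents do not establish that it does.

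**The case against.** The best defence is that 3.2 describes both a 2-year endpoint and follow-on to the end of the trial, and that the wording in 7.2 echoes the follow-on part. Section 3.2 would then supply the time point and 7.2 the variable, and one clarifying line would be enough. It is true that the intended primary time is recoverable and the repair is small. But if 7.2 describes the durability analysis, the 2-year endpoint has no analysis at all; and if 7.2 describes the primary analysis, its window is the wrong one.

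On the denominator, simple and complex prevention are names of assigned packages, so *treated with* may mean *assigned to*. Section 7.3 also speaks of participants and allocation rather than lesions. Both points stand, and so this part is an ambiguity to remove, not a demonstrated breach of intent to treat.

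Three stronger readings are tempting and unsupported:
- A reader might infer that the unequal windows unbalance the arms. Section 6.5.1 randomizes schools in pairs within each year's set, so the arms are balanced by wave.
- A reader might infer that the treated-lesion set favours simple prevention. Neither the size nor the direction of any effect can be derived.
- A reader might infer that 7.2 costs power. That depends on reading attrition as permanent dropout, and the gap vanishes under the other reading.

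**Conclusion.** The time-point conflict is real and concerns a primary outcome: 2 years in 3.2 and 3.1, against a window of 5 years, 4 years or less in 7.2, with one 10-point margin for both. This rests on the text alone and needs no assumption. How far the two results would differ is unknown; the persistence figures above only show that the levels could differ materially.

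The departure from 7.3 is conditional on reading *treated* as care delivered to the lesion. A difference between arms is possible, not shown. The retention figures (41% at 2 years against 21% or 13% at the last visit) are an illustration under permanent dropout, and the case for change does not rest on them. The stated sample size of 9,662 follows correctly from its inputs.

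**What to change.** In 7.2:
- Define the primary arrest outcome at the 2-year examination, with a stated visit window.
- Use carious lesions recorded at the child's first examination, in both arms, whether or not each lesion was treated.
- Analyse children as randomized, and state how those without a 2-year examination are handled, including those who join too late to reach it.
- Make arrest sustained to the end of the study a secondary durability analysis.
- Apply one scoring rule for arrest in both arms, covering filled, sealed and lost teeth, and fix it while the analysts are blinded. Section 3.2 describes arrest by colour and hardness, so how to score a covered surface is a choice for the sponsor to make and record.
- Give a posterior-only lesion set as a sensitivity analysis.

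The cost is SAP wording, the decision on scoring, some derivation from examination records already collected under 6.1.6, and one sensitivity analysis. There are two downsides: an all-lesion set may be less favourable to simple prevention, and lesions first seen at later visits leave the primary analysis.

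Separately, the sponsor must reconcile the Study Summary and sections 1.3, 5.8.3, 6.2.1, 6.2.2, 6.3 and 6.6 on which lesions are treated. No change of care is proposed.
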